## 10.6 CV Physical Examination

CV physical examination findings will be listed and summarized. Summaries will show the number of subjects with each condition and other condition-specific details, if applicable. Shifts from baseline in present/absent indicators will also be summarized, if appropriate.

## 10.7 Vital Signs, Height, Weight, and Body Mass Index (BMI)

Vital signs will include systolic and diastolic blood pressure, heart rate, respiratory rate, and body temperature. Listings of vital signs, height, weight, and BMI will include study visit, date and time of collection, and observed values. Observed values and changes from baseline will be summarized. BMI will be calculated as:

$$BMI = \frac{weight \ (kg)}{(height \ (m))^2}$$

using baseline height.

Prior to summarizing, unit standardization may be required and will be done as follows:

- Temperature recorded in degrees F will be converted to degrees C as  $C = 5(F-32)/9$ .
- Height recorded in inches will be converted to centimeters by multiplying by 2.54.
- Weight recorded in pounds will be converted to kilograms by multiplying by 0.454.

## 10.8 12-Lead ECG

Listings of 12-lead ECG parameters will include study visit, date and time of ECG, and observed values. Observed values and changes from baseline in ventricular rate and interval parameters (QRS, PR, QT, QTcB, QTcF) will be summarized.

Bazett's correction (QTcB) will be calculated as:

$$QTcB = QT / \sqrt{60/HR} ,$$

and Fridericia's correction (QTcF) as:

$$QTcF = QT / \sqrt[3]{60/HR}$$

where HR = ventricular rate.

Summaries of 12-lead ECG parameters will also include normal sinus rhythm indicator, specific rhythms, premature atrial contractions indicator, details of premature ventricular contractions and heart block and conduction abnormalities, and overall interpretation.

## 10.9 24-Hour Ambulatory ECG Monitoring

Listings of 24-hour ambulatory ECG parameters will include study visit, start and end dates and times, and observed values. Observed values and changes from baseline in heart rate (mean, minimum, maximum) number of premature atrial contractions over 24 hours, and number of premature ventricular contractions over 24 hours will be summarized. Summaries will also include indicators for sinus rhythm (normal sinus, sinus bradycardia, sinus tachycardia), atrial fibrillation, atrial flutter, junctional rhythm, heart block abnormalities, conduction defects, asystole, supraventricular tachycardia, ventricular tachycardia, ventricular fibrillation, and overall interpretation. Other details regarding the presence of these events will be included in the listings.

## 10.10 Echocardiography

An echocardiogram will be performed at screening and Month 1 only. Echocardiography will be performed to measure the size and shape of the heart, its chambers and blood flow as well as valvular structure and function. Additionally, the echocardiogram will be used for detection of new abnormalities that may be indicative of myocarditis.

The following echocardiographic indices will be listed and summarized:

- LVEDV
- LVESV
- LV end diastolic diameter (LVEDD)
- LV end systolic diameter (LVESD)
- LVEF
- LV fractional shortening, calculated as  $100 \times (LVEDD - LVESD) / LVEDD$ .

# 11. OTHER DATA COLLECTED

## 11.1 Missed Visits and Assessments

A listing will be provided of missed visits and assessments.

## 11.2 Protocol Violations/Deviations

Protocol discrepancies will be classified as either violations or deviations. Per ICH E3 (Structure and Content of Clinical Study Reports), violations will be defined as:

- Enrolling into the trial without meeting all inclusion/exclusion criteria and without obtaining a waiver for any deviations from the protocol-defined entry criteria;
- Continuing in the trial after developing a withdrawal criterion (see Protocol Section 7.5);
- Receiving an incorrect dose or incorrect treatment; or
- Taking a prohibited concomitant medication (see Protocol Section 5.4).

Subjects with protocol violations will be excluded from the per protocol population. All other protocol discrepancies will be considered deviations and will be categorized for purposes of

summarization. Some protocol deviations may prohibit subjects from being in the per protocol population; this will be determined before database lock.

In addition to the listings of inclusion/exclusion criteria detailed in [Section 8.2](#) and missed visits and assessments detailed in [Section 11.1](#), a separate listing will show all other protocol violations/deviations and will include protocol version, the category of the violation/deviation (to be determined), a description of the violation/deviation, and an indicator for per protocol exclusion (to be determined). Frequency and percentage of subjects by classification and category will be summarized.

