cardiac MRI unless: a) the subject's efficacy procedures including baseline cardiac MRI were conducted within 28 days of infusion; **or**, b) the subject's efficacy procedures including baseline cardiac MRI were conducted \geq 60 days post-MI **and** within 60 days of infusion.

Protocol safety procedures are defined as:

- Medical history, limited physical examination, and cardiac physical examination
- Medication review
- Vital signs
- 12-Lead ECG
- Laboratory tests: hematology, chemistry, urinalysis, hemoglobin A1c (HbA1c), serum NT- proBNP, Serum β - HCG (only for females who are not diagnosed as postmenopausal), HIV and hepatitis screens, and serum for biomarkers (if subject has provided consent); refer to [Table 1](#) for comprehensive list of laboratory tests
- 24 hour ambulatory ECG monitoring
- Adverse event assessment

Protocol efficacy procedures are defined as:

- Laboratory tests: serum NT- proBNP HLA typing, DSA evaluation, ELISpot Assay sample
- Echocardiography
- Cardiac MRI
- NYHA functional class assessment
- Six Minute Walk Test
- MLHFQ
- SF-36 health survey
- WPAI:SHP questionnaire
- Patient Global Assessment

Randomization will occur after all of the screening examinations have been completed and only if the subject continues to meet all of the eligibility criteria. After the subject is randomized, the subject must continue to meet eligibility criteria before proceeding to intracoronary infusion.

Sites should randomize eligible subjects at least three (3) working days **prior** to a subject's scheduled infusion date. The Sponsor should be notified of cases that prevent randomization at least three (3) working days prior to a subject's scheduled infusion date (e.g., timing of MRI results). Subjects who are not randomized and do not proceed to infusion due to violation of eligibility criteria at screening will be withdrawn from the study as screen failures and will have no further follow up.

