10.9 Protocol Violations/Deviations

As they occur, protocol violations (i.e., events that have potential to impact interpretation of data for intended population, such as violations of inclusion/exclusion criteria) and deviations (i.e., variations from protocol-specified processes unlikely to impact interpretation of data for intended population) will be documented at each site and reported to the Sponsor. Upon detection of a violation, the Sponsor will ensure reporting to the proper local and federal regulatory authorities in accordance with all applicable federal and local regulations. The Sponsor will determine the course of action based on the severity of the deviation or violation. These may include but are not limited to, withdrawal of the subject, additional training at the site, additional site monitoring, etc. In addition, the medical director and statistician will review the circumstances of each violation (in a blinded fashion) to determine whether the data can reasonably be included in the per protocol final analysis.

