## 6. ANALYSIS POPULATIONS

The following analysis populations are defined for the trial:

**Primary Safety Population:** All subjects in the Primary Randomization Cohort who received the IP. Subjects will be summarized and analyzed per treatment actually received, regardless of their randomization assignment.

**Primary Intent-to-Treat (ITT) Population:** All subjects in the Primary Randomization Cohort who were randomized. Subjects will be summarized and analyzed per their randomization assignment, regardless of the treatment actually received.

**Primary Modified Intent-to-Treat (mITT) Population:** For a given efficacy parameter, all subjects in the Primary Randomization Cohort who received the IP, had a baseline observation and at

least one post-baseline observation. Subjects will be summarized and analyzed per their randomization assignment, regardless of the treatment actually received.

Per Protocol Population: Subjects in the Primary Randomization Cohort with no major protocol violations at end of study (EOS). The list of subjects with major protocol violations will be compiled in a blinded fashion prior to database lock at EOS. For the analysis of the primary efficacy endpoint based on the per protocol population, a sensitivity analysis will be done to evaluate the effect of excluding subjects randomized in the wrong cohort or the wrong stratum from the per protocol population; i.e., subjects incorrectly randomized in the Exploratory Randomization Cohort would be excluded from the per-protocol sensitivity analysis, as would subjects randomized in the wrong stratum based on time since index MI (recent vs. chronic).

Exploratory Safety Population: All subjects in the Exploratory Randomization Cohort who received the IP. Subjects will be summarized and analyzed per treatment actually received, regardless of their randomization assignment.

Exploratory ITT Population: All subjects in the Exploratory Randomization Cohort who were randomized. Subjects will be summarized and analyzed per their randomization assignment, regardless of the treatment actually received.

Exploratory mITT Population: For a given parameter, all subjects in the Exploratory Randomization Cohort who received the IP, had a baseline observation and at least one post-baseline observation. Subjects will be summarized and analyzed per their randomization assignment, regardless of the treatment actually received.

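### Two per-protocol rules in the SAP need correcting: the wrong-cohort exclusion as spelled out removes nobody, and waived ineligibility is exempted from being a violation although Protocol 10.9 has no such exemption

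*SAP*

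**What the plan says.** **Who is in the per-protocol population.** SAP 6 defines it as "Subjects in the Primary Randomization Cohort with no major protocol violations at end of study (EOS". The list of major violations is to be compiled blinded before database lock. SAP 11.2 does not use the word major; it says "Subjects with protocol violations will be excluded from the per protocol population".

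**Wrong cohort.** For the primary endpoint in this population, SAP 6 states that "a sensitivity analysis will be done to evaluate the effect of excluding subjects randomized in the wrong cohort or the wrong stratum". It then explains what that means: "subjects incorrectly randomized in the Exploratory Randomization Cohort would be excluded from the per-protocol sensitivity analysis", and likewise subjects in the wrong time-since-MI stratum. SAP 7.4 repeats the wrong-stratum analyses but not the wrong-cohort one.

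**Eligibility.** The first violation listed in SAP 11.2 is "Enrolling into the trial without meeting all inclusion/exclusion criteria and without obtaining a waiver for any deviations from the protocol-defined entry criteria". Every other discrepancy is a deviation, and "Some protocol deviations may prohibit subjects from being in the per protocol population; this will be determined before database lock". SAP 8.2 plans to list unmet criteria and any waivers.

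**Protocol.** Protocol 10.9 describes violations as events that could affect interpretation, "such as violations of inclusion/exclusion criteria", without a waiver exception. The medical director and statistician then review each one blinded to decide whether the data can go into the per-protocol analysis. Protocol 7.1 allows randomization "only if the subject continues to meet all of the eligibility criteria". SAP 14 reports no deviations from the protocol's statistical methods.

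**The concern.** A per-protocol analysis is informative only if its membership rules remove the subjects they are meant to remove, and do so by rules fixed in advance. Two of the rules here do not clearly do that.

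The cohort split rests on DSA status: matched subjects belong in the Primary Cohort, and subjects with antibodies to every available donor belong in the Exploratory Cohort. The misassignment that could affect a Primary Cohort result is therefore a mismatched subject randomized into it. The SAP's explanation names the reverse error instead.

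For eligibility, the SAP makes violation status depend on whether a waiver was obtained, a condition the protocol does not have. Two subjects who fail the same criterion can then be treated differently in the per-protocol set because of paperwork rather than clinical state.

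At stake is which subjects a planned supportive analysis drops, and whether two programmers reading the SAP would drop the same ones.

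**Working it through.** The point concerns set membership, so there is no planned figure to reproduce. The check follows three kinds of subject through SAP 6, 7.4 and 11.2 and Protocol 5.1.1, 7.1 and 10.9.

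**A. Matched subject randomized into the Exploratory Cohort by mistake.**
- SAP 6 restricts the per-protocol population to the Primary Cohort, so this subject is already outside it.
- The exclusion spelled out in SAP 6 names this subject, so as written it removes nobody.
- The rule could remove someone only if such subjects were first moved into the Primary Cohort for analysis. SAP 7.4 gives a rule of that kind for strata (reclassify by time since MI). No corresponding rule exists for cohorts.

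**B. Subject with DSAs to all available donors randomized into the Primary Cohort.**
- In the per-protocol population by definition, unless another rule applies.
- Eligibility bullet of SAP 11.2: does not apply. Protocol 5.1.1 says DSAs do not exclude a subject from the study.
- Incorrect-treatment bullet of SAP 11.2: not clearly applicable. If stretched to cover cells from an incompatible donor, it would reach CAP-1002 subjects but not equally mismatched placebo subjects, so the exclusion would differ by arm.
- Wrong-cohort sensitivity analysis of SAP 6: the general phrase covers this subject; the explanation that follows does not name this direction.
- Deviation clause of SAP 11.2: could remove the subject, but no criteria are given.

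**C. Subject who failed an entry criterion and had a waiver.**
- SAP 11.2 requires two conditions for a violation: ineligible, and no waiver. The second is not met, so the subject is a deviation.
- Result under the SAP: retained by default, removable only through the deviation clause.
- Result under Protocol 10.9: a violation, sent to blinded case-by-case review.

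| Subject | SAP | Protocol 10.9 |
|---|---|---|
| Ineligible, no waiver | violation, excluded automatically | violation, blinded review decides |
| Ineligible, waiver | deviation, kept by default | violation, blinded review decides |

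The two documents differ in both rows and in opposite directions: the SAP is stricter without a waiver and looser with one.

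**Size.** Neither document gives a number of waivers or cohort errors. Only the weight of one subject can be shown. Assume the 93 completers of Protocol 9.2 split evenly by stratum and 2:1 by arm: 93/2 is about 46 per stratum, of whom about 15 are on placebo. One subject is then 1/46 = 2.2% of a stratum, or 1/15 = 6.7% of its placebo arm. This holds for any subject and does not estimate bias.

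**The case against.** The strongest reply is that both rules have a safety net. SAP 11.2 lets deviations lead to exclusion, decided before lock, and SAP 6 has the major-violation list compiled blinded. A waived subject can therefore be removed, and SAP 8.2 makes every waiver visible. The governing sentence on wrong cohort gives no direction, so the explanation after it may be a drafting slip. SAP 5 requires DSA results and identification of compatible donor lines before randomization, which should make cohort errors uncommon. Baseline DSA may also be examined as a subgroup or covariate (SAP 7.4 and 9).

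Much of this stands, and it rules out three stronger readings that a reader might infer:

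- *The plan keeps waived ineligible subjects.* The documents support only that they are kept by default, subject to a later decision without criteria.
- *The per-protocol check fails altogether.* The rules on unwaived ineligibility, incorrect dose or treatment, prohibited medication and continuing after a withdrawal criterion all operate, as do the wrong-stratum analyses.
- *Every eligibility breach should simply be excluded.* Protocol 10.9 provides for blinded review, not automatic exclusion, so that remedy would itself depart from the protocol unless the two are reconciled.

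What the reply does not remove: a pre-lock decision without criteria is discretion rather than a rule; the only spelled-out content of the wrong-cohort exclusion is empty; and the waiver condition has no counterpart in Protocol 10.9, while SAP 14 declares no differences.

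**Conclusion.** The point holds as two defects of definition in supportive analyses. As spelled out, the wrong-cohort exclusion in SAP 6 removes no one and does not name the misassigned subject who would be in the population. The waiver condition in SAP 11.2 conflicts with the classification in Protocol 10.9, and the conflict is not declared in SAP 14. The undefined word major in SAP 6, absent from SAP 11.2, adds to the uncertainty about who is excluded.

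The size of the effect cannot be stated, because no count of affected subjects is given. The primary efficacy analysis uses the mITT population, and SAP 9 says secondary analyses in other populations may be done, so the primary estimate, the alpha and the success rule do not depend on this. The conclusion on the cohort rule rests on taking the explanatory clause in SAP 6 at its word. If the general phrase governs, the intention is sound and only the wording fails. Correction is still worthwhile, because it settles which subjects a planned sensitivity analysis removes.

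**What to change.** **SAP 6.** Replace the explanatory clause on cohorts with: subjects with DSAs to all available donors at screening who were randomized in the Primary Randomized Cohort. Apply it to both arms. List separately any matched subjects wrongly randomized in the Exploratory Cohort.

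**SAP 11.2.** Remove the waiver exemption, so that waived breaches are classed as violations. Then reconcile automatic exclusion with the blinded review in Protocol 10.9. Alternatively, add a per-protocol sensitivity analysis that excludes waived subjects.

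**Both sections.** Use one definition of a major violation.

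**SAP 14.** Record any difference from Protocol 10.9 that remains.

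The cost is a few sentences of SAP text before database lock and, at most, a few fewer subjects in a supportive analysis.

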## 12. CLINICAL EVENTS COMMITTEE

In order to apply some level of consistency and standardization, the following will be adjudicated by a CEC:

- Primary and secondary safety endpoints with the following exceptions:
  - The CEC will refer any potential case of acute myocarditis to the DSMB in order to make a final ruling on whether the clinical event meets the protocol-defined definition of acute myocarditis. The DSMB will be unblinded to humoral and cellular immunology data.
  - Development of increased anti-HLA antibody levels with development of sensitization to HLA antigens specific to the CAP-1002 CDC donor. The DSMB clinical immunologist will be unblinded to all available DSA data during the conduct of the trial.
- AEs occurring within 24 hours of IP administration.
- AEs judged by the investigator as possibly, probably or definitely related to the IP or IP administration procedure, reported at any time.
- Treatment-emergent SAEs.

The CEC will follow consensus definitions of CV endpoint events. In the case where the protocol explicitly provides an endpoint definition, the CEC will adjudicate the clinical event according to the protocol definition and then, separately, according to the consensus definition. In the case where the protocol provides only a partial definition (e.g., “emergency room treatment for heart failure”) or is silent on the definition of the endpoint, the consensus definition, if it exists, will be used.

For safety endpoints, a hierarchy will be applied for a clinical event that could be adjudicated in multiple categories so that a clinical event is counted only once. The hierarchy, from highest severity to lowest, will be death > heart failure hospitalization > CV-related hospitalization. Any adjudicated event not otherwise named in the consensus definitions will be MedDRA-coded.

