5.3 Blinding

Subjects will be randomized 2:1 favoring CAP-1002 in a double-blind fashion, with both the Investigators and the subjects blind to treatment received. Central reviewers interpreting the MRI data and the laboratory studies will also be blinded to group assignment.

During the ALLSTAR blinded Primary Randomized Cohort an independent storage/distribution center will be used to distribute IP (CAP-1002 and placebo) doses to the clinical sites. The administration of the blinding process will occur at this independent storage/distribution center to remove Capricor personnel from this process. The distribution and back-up drug product return will occur in validated vapor phase liquid nitrogen (N2) shipping containers allowing for consistent transportation and scheduling flexibility at all sites.

Both CAP-1002 and the placebo will be packaged in identical cryogenic bags with similar labels. At the clinical site, the IP is thawed to room temperature, prepared and drawn into masked (with amber/transparent tape) syringes. The amber/transparent tape will allow the treating physician to see air bubbles but obscure the clear cellular suspension. Specific instructions for use will be included with each product.

A central laboratory will be used to assess the sensitization to products, (i.e., DSAs, ELISpot assay); the results will not be shared with the Investigator or site study personnel or Sponsor staff to preserve blinding.

A DSMB will be utilized for this study and will have access to unblinded data. An interim analysis of the final 6 months data will be completed when subjects complete the 6 month follow-up visit. Only a statistician independent of the clinical trial team will have access to unblinded data and immunological test results prior to the interim analysis; this individual will provide the unblinded reports to the DSMB.

Subjects, investigators, and Sponsor's personnel who had direct responsibility for monitoring at the sites will be blinded throughout the study. The interim analysis will be considered an administrative interim analysis planned for the determination of efficacy at 6 months, the appropriate Sponsor representatives will be unblinded in order to review and make decisions regarding entry into Phase III clinical development. A list will be maintained in the trial master file to track any persons unblinded during the trial.

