The Investigator will attempt to establish a diagnosis of the event based on signs, symptoms, and/or other clinical information. In such cases, the diagnosis should be documented as the AE/SAE and not the individual signs and symptoms.

Adverse events classified by the Investigator as related to investigational product or the administration procedure, potential safety endpoints and MACEs are adjudicated by the Clinical Endpoints Committee (CEC). Detailed information on the CEC adjudication process can be found in the Clinical & Adverse Event Reporting & Adjudication Procedures Manual.

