### 2.3 Study Endpoints and Hypotheses

#### 2.3.1 Primary Safety Endpoint

The primary safety endpoint is whether or not any of the following adjudicated (see [Section 12](#)) events occur during the one month post intracoronary infusion:

1. Acute myocarditis possibly attributable to the investigational product (IP), diagnosed with consideration of clinical context, with or without a clinically indicated endomyocardial biopsy. In order to be considered related to the IP, humoral or cellular immune reaction specific to CAP-1002 must also be documented for subjects treated with CAP-1002, or a temporal relationship with IP administration must exist for subjects administered placebo. See [Section 12](#) for further information related to blinded adjudication by the Clinical Events Committee (CEC).
2. Death due to ventricular tachycardia or ventricular fibrillation defined as occurring with electrocardiogram (ECG) documentation of these arrhythmias during ambulatory ECG monitoring in an outpatient setting or during routine ECG monitoring while hospitalized.
3. Sudden unexpected death defined as occurring within one hour of symptom onset, or unwitnessed death in a person previously observed to be well within the preceding 24 hours without an identified cause.
4. Major adverse cardiac event (MACE), defined as the composite incidence of death, nonfatal recurrent MI, hospitalization with primary discharge diagnosis of heart failure, emergency room treatment for heart failure [ N-terminal pro-hormone brain natriuretic peptide (NT-proBNP)  $> 450$  pg/mL or brain natriuretic peptide (BNP)  $> 100$  pg/ml, with treatment including intravenous diuretic administration], LV assist device (LVAD) placement or heart transplant. Peri-infusion MI will be defined as presence of troponin or creatine phosphokinase MB isoenzyme (CK-MB) levels  $> 5$  times the upper reference limit during the 24 hours following infusion. These elevations must be accompanied by symptoms of ischemia  $> 20$  minutes in duration and ECG changes indicative of new ischemia (new ST-T changes or new left bundle branch block), development of pathological Q waves on the ECG, imaging evidence of new loss of viable myocardium, or new regional wall motion abnormality.

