The distribution of IP will occur in validated dry vapor shippers allowing for consistent transportation and scheduling flexibility at all sites. Both CAP-1002 and placebo will be packaged in identical cryogenic bags with similar labels. At the clinical site, the IP is thawed to room temperature, prepared and drawn into masked (with amber/transparent tape) syringes. The amber/transparent tape will allow the treating physician to see air bubbles but obscure the clarity of the IP suspension. Specific instructions for use are provided to each investigative site for reference. Central laboratories will be used to assess sensitization to CAP-1002 [i.e., single antigen bead (SAB), enzyme-linked immunosorbent spot (ELISpot) assay]. Because these results may unblind, they will not be shared with investigators, subjects, site personnel, or Sponsor staff in order to preserve blinding.

The DSMB, including a statistician independent of the sponsor's clinical trial team, will have access to unblinded data and immunological test results. In addition, as a result of administrative interim efficacy analyses (see [Section 13.2.2](#)), a prespecified group of personnel from the Sponsor (the smallest group possible), as well as personnel from Janssen Biotech, Inc. ("Janssen") in order to comply with the terms of that certain Collaboration Agreement and License Option, will become unblinded and will have full access to the efficacy data.

A list will be maintained in the trial master file to track any persons unblinded during the trial.

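### The final ruling on acute myocarditis, including the clinical diagnosis, rests with the unblinded DSMB, and neither document has the blinded CEC record that diagnosis first

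*SAP*

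**What the plan says.** The documents describe the adjudication of acute myocarditis in several places.

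- **SAP 2.3.1, item 1** (primary safety endpoint, one month) points to Section 12 for "further information related to blinded adjudication by the Clinical Events Committee (CEC"). SAP 2.3.3, item 1, gives the same pointer for the twelve-month endpoint.
- **SAP 5** keeps the CEC blinded for the whole trial.
- **Protocol 7.4** says that "potential safety endpoints and MACEs are adjudicated by the Clinical Endpoints Committee (CEC"), and mentions no exception for myocarditis.
- **SAP 12** lists myocarditis among the exceptions to CEC adjudication: "The CEC will refer any potential case of acute myocarditis to the DSMB in order to make a final ruling". The ruling is "on whether the clinical event meets the protocol-defined definition of acute myocarditis". The section adds: "The DSMB will be unblinded to humoral and cellular immunology data".
- **On what the DSMB knows**, SAP 5 says that it "will have access to unblinded data and immunological test results", and Protocol 5.3 says "A DSMB will be utilized for this study and will have access to unblinded data".

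The definition in SAP 2.3.1 has two parts. The first is a diagnosis made in the light of the clinical picture, with biopsy only where clinically indicated. The second is attribution to the product. For a CAP-1002 subject this needs a documented humoral or cellular response to the product; for a placebo subject it needs a temporal relationship with administration.

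**The concern.** A reader who follows the pointer to SAP 12 expects a blinded ruling and finds an unblinded one. The ruling covers the clinical event itself, not just attribution. Whether a troponin rise, a new wall-motion abnormality and symptoms amount to myocarditis is a matter of opinion, and knowing the arm can sway it. For an allogeneic cell product, knowledge of CAP-1002 treatment could make a board readier to call myocarditis, or more cautious about doing so. The direction cannot be predicted.

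Two features add to this. The DSMB also reviews tests of the primary safety endpoint and advises on continuation (SAP 13.2.1), so it would rule on a component of the endpoint it monitors. And myocarditis is not in the MACE definition, so a case with no other listed event enters the composite only through this ruling. Protocol 3.2 itself names bias in the scoring of events as a reason for blinding.

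**Working it through.** **1. Which part of the definition needs the arm?**

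| Element | Needs the arm or immunology data? | Who rules under SAP 12 |
|---|---|---|
| Is there a potential case? | No | Blinded CEC (refers it) |
| Is it acute myocarditis? | No | DSMB |
| Did it fall within the window? | No | DSMB |
| Attribution, CAP-1002: immune response | Yes | DSMB |
| Attribution, placebo: temporal relationship | Yes, to know that this criterion applies | DSMB |

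The second and third rows need no treatment knowledge, yet they sit with the unblinded body. Neither document has the CEC record a diagnosis before it refers the case.

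**2. How much can one ruling move the composite?** The plan gives no figure for this, so there is none to reproduce. The inputs are 69 CAP-1002 and about 34 placebo subjects in the Primary Randomized Cohort (Protocol synopsis, Study Population). The rule is that the upper limit of the 90% CI for the difference must be below 0.20 (SAP 2.3.2), with a Wald test (SAP 10.1).

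- One CAP-1002 case: 1/69 = 1.45 points.
- One placebo case: 1/34 = 2.94 points.

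Both hold only if the subject has no other component event.

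Upper limit = (p_c − p_p) + 1.645 × √[p_c(1 − p_c)/69 + p_p(1 − p_p)/34].

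| CAP-1002 events | Placebo events | Upper limit | Below 0.20? |
|---|---|---|---|
| 9 | 0 | 0.197 | Yes |
| 10 | 0 | 0.215 | No |
| 11 | 2 | 0.199 | Yes |
| 12 | 2 | 0.215 | No |

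For the first row, 9/69 = 0.1304, SE = √(0.1304 × 0.8696/69) = 0.0405, and 0.1304 + 1.645 × 0.0405 = 0.197. One ruling can change the conclusion only near such counts, that is, at a CAP-1002 rate of 13% or more (9/69 = 13.0%). At low counts it cannot: with no placebo events, going from 2 to 3 CAP-1002 events moves the limit from 0.062 to 0.084.

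**3. Can attribution be applied from what is already specified?** Not fully. The SAP uses two DSA thresholds, 5000 and 1000 MFI, but for a different endpoint (HLA sensitisation, SAP 2.3.3 item 10 and SAP 10.2), and designates neither for myocarditis. ELISpot has a positivity rule (value above 3, SAP 10.5), but Protocol 6.5.2 plans it at screening and one month only, in 36 randomized CAP-1002 and 18 randomized placebo subjects unless the DSMB extends it. At least 69 − 36 = 33 planned CAP-1002 subjects would then have no cellular result. A humoral response alone is enough, so the gap matters where DSA is not raised.

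**The case against.** The strongest reply is that the referral has a sound reason. The definition differs by arm, the immunology results could unblind, and the CEC must stay blinded, so a blinded CEC cannot apply the full definition. Passing the case to an independent body that is already unblinded protects the CEC. This stands for attribution, and it means that simply handing the whole ruling back to the CEC would not work. It does not justify leaving the diagnosis unblinded as well.

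Other points also stand in part:

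- A reader might infer that the SAP breaks a promise of blinded adjudication. The text does not support that. SAP 2.3.1 only cross-refers to Section 12, and Section 12 openly declares the exception. The fault is that the sections do not agree.
- The blinded CEC still identifies the cases. It also adjudicates treatment-emergent SAEs, events within 24 hours of administration and events judged related, so many myocarditis cases would come before it by another route. That is not a recorded ruling on myocarditis as an endpoint.
- Components are listed and summarised singly (SAP 10.1), so the composite can be recomputed without myocarditis. That shows how much depends on these cases, but supplies no blinded diagnosis.
- The adjudication procedures manual and the DSMB charter are not available here. Either may already require a CEC opinion before referral. The finding is confined to the protocol and SAP.

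**Conclusion.** The concern holds as a question of who judges what, and with which knowledge. SAP 12 exposes the clinical diagnosis of a primary safety component to bias that could be avoided, and SAP 2.3.1, SAP 2.3.3 and Protocol 7.4 do not agree with it.

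The numerical effect is probably small. This rests on an assumption that few myocarditis cases will occur, since the documents give no rate, and on the fact that a case changes the composite only in a subject with no other component event. The tipping counts in the table might be read as evidence that one ruling is likely to decide the primary safety test. The documents do not support that: nothing in them points to a CAP-1002 event rate of 13% or more. Nor do they support any direction of bias. What is mainly at stake is the credibility of the myocarditis comparison, which is reported by arm in its own right.

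**What to change.** Amend SAP 12 as follows.

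1. Before referral, the blinded CEC decides and locks whether the event is acute myocarditis and whether it fell within the endpoint window (one month or twelve months).
2. The DSMB then applies only the attribution criterion, namely immune response for CAP-1002 and temporal relationship for placebo, as a separate recorded step. It does not revise the CEC's clinical ruling.
3. State in advance which DSA threshold governs this step and what applies when no ELISpot result exists. The placebo criterion still calls for judgement by someone who knows the arm, which is one reason for the next item.
4. Report the primary safety composite also with myocarditis as diagnosed by the blinded CEC alone, regardless of attribution.
5. Reconcile SAP 2.3.1, 2.3.3 and 12 with Protocol 7.4, and align the adjudication manual and DSMB charter if they differ.

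The cost is wording, two recorded steps per potential case and one extra sensitivity summary. Both committees already exist, no new data are collected, and the DSMB keeps its unblinded safety role.
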